6.3.1.3 Dose adjustment for elevated AST, ALT, and T-Bil levels

When an increase in AST, ALT, and/or T-Bil levels is observed during regorafenib treatment for which a causal relationship cannot be ruled out, the dose will be adjusted with reference to "Table 5: Dose adjustments for elevated AST, ALT, and T-Bil levels."

It is recommended to conduct liver function tests at least once a week until the liver function test results return to within the normal range or return to the grade at the time of enrollment.

| NC | I CTCAE Grade | Expression times | Dose adjustment |
|---------|---|--------------------------|--|
| Grade 2 | T-Bil exceeds 1.5 times the normal value upper limit and 3 times or less If AST or ALT exceeds 3 times the normal value upper limit and is 5 times or less | Regardless of the number | Continue administration and continue at least once a week for at least 4 weeks until T-Bil is less than 1.5 times the upper limit of normal value, AST or ALT is less than 3 times upper limit of normal value or recovered to Grade before administration, AST, ALT And T - Bil measurement should be carried out. |
| Grade 3 | T-Bil exceeds 3 times the normal value upper limit and is 10 times or less If AST or ALT exceeds 5 times the normal value upper limit and is 20 times or less | First time | Regorafenib is withdrawn until T-Bil is less than 1.5 times the upper limit of normal value and AST or ALT is recovered to less than 3 times normal value upper limit or below registered Grade. When dosing is resumed, it is recommended to reduce the same amount or 1 level and measure AST, ALT and T-Bil once a week for a minimum of 4 weeks. |
| | | Second time | Discontinue administration. |
| Grade 4 | T-Bil exceeds the normal value upper limit by 10 times AST or ALT is over 20 times the normal value upper limit | Regardless of the number | Discontinue administration. |

Table 5: Dose adjustment for elevated AST, ALT, and T-Bil levels

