| | Tumours (RECIST) version. 1.1, and immune-related (ir) RECIST |
| | - Progression-free survival (PFS) |
| | - Overall survival (OS) |
| | - Disease control rate (DCR) |
| | Exploratory items (performed as accompanying research in the present trial): |
| | Tests of various biomarkers |
| Trial design | The present trial is a phase I clinical trial intended to evaluate the safety of regorafenib |

| | and nivolumab combination therapy in patients with unresectable recurrent solid |
|-------------|---|
| | tumors who are refractory or intolerant to standard chemotherapy. |
| Trial study | Inclusion criteria |
| population | 1. Patients who provided written informed consent to be subjects in this trial |
| | 2. Patients at least 20 years of age on the day of providing consent |
| | 3. Dose-escalation cohort: Patients with histologically or cytologically confirmed |
| | advanced or metastatic solid tumors. |
| | Expansion cohort: Patients with histologically or cytologically confirmed |
| | advanced or metastatic solid tumors (gastric, colorectal, or hepatocellular cancer). |
| | 4. Patients with an Eastern Cooperative Oncology Group (ECOG) performance |
| | status (PS) of 0 or 1 |
| | 5. Patients capable of taking oral medication |
| | 6. Patients with evaluable or measurable lesions as per RECIST version 1.1 |
| | 7. Patients with adequate organ function at the time of enrollment as defined below: |
| | [Acceptable 7 days examination before the same day of the registration date] |
| | • Neutrophil count ≥ 1500 mm ³ |
| | • Platelet count $\geq 10.0 \times 10^4$ /mm ³ |
| | • Hemoglobin (Hb) \geq 9 g/dL, |
| | - aspartate transaminase (AST), alanine transaminase (ALT) $\leq 100 \text{ U/L}$ ($\leq 100 \text{ U/L}$ in |
| | patients with Hepatocelular carcinoma, ≤ 250 U/L in patients with liver metastasis) |
| | • Total bilirubin \leq 1.5mg/dLtimes the upper limit of normal |
| | • Creatinine ≤1.5mg /dL |
| | • Urinary protein: It satisfies one of the following (if any of the inspection criteria are |
| | satisfied, other examination may not be carried out) |
| | (i) urinary protein (test paper method) is 2+ or less |
| | (ii) UPC (Urine Protein Creatinine) ratio <3.5 |
| | (iii) 24-hour urine protein was measured, urinary protein $\leq 3500 \text{ mg}$ |
| | • PT-INR: ≤ 1.5 (≤ 3.0 in case of anticoagulant administration) |
| | * It is Child A in the case of Expansion cohort's hepatocellular carcinoma |

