5.2 Important notes regarding enrollment

- 1) Enrollments after the initiation of the treatment protocol will not be permitted without exception.
- 2) When the enrollment and eligibility checklist content is unsatisfactory, the enrollment will not be accepted until it is all the content is satisfied.
- 3) After confirmation of eligibility, a registration number will be issued. Enrollment will be completed once the registration number has been issued.
- 4) Except in the event of withdrawal of consent, including the refusal of the use of data in the trial, patients will not be removed from the trial (erased from the database) once they have been enrolled. In the event of a double registration, the information from the first enrollment (registration number) will be used.

- 5) When a misregistration or double registration is discovered, the data management office should be contacted as soon as possible.
- 6) At the time of enrollment, in the event of an ongoing medical examination at another hospital or department, the attending physician is to be contacted and notified that the patient concerned is participating in the present trial.

6 Dosing schedule and combination therapy

If the safety of the subject is not at risk, treatment and changes to treatment will be carried out in accordance with the content of this chapter. If a medical emergency is identified when the present protocol is followed, the treatment will be changed in accordance the medical judgment of the principal investigator (or subinvestigator) for the trial (hereinafter "principal investigator").

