6.1 Protocol treatment

In the present trial, the protocol treatment will consist of the investigational drug, nivolumab, used in combination with regorafenib. However, in the event that the termination criteria are satisfied for one of these drugs, the trial investigator can consider continuing the treatment protocol with either nivolumab or regorafenib monotherapy upon deliberation with the trial coordinating committee. The treatment protocol will commence within 14 days of enrollment, including the day of enrollment. Furthermore, in the event that administration of the investigational drug cannot be initiated within 14 days of enrollment (including the day of enrollment), the trial coordinating committee is to be contacted to examine how the patient should be handled.

The following terminology is used in the present protocol:

- Termination: Administration of the investigational drug is not resumed.
- Washout: Omission of one or more doses of the investigational drug and moving onto the next dosing schedule.

• Washout period: The duration of time that the investigational drug is not administered.

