6.3.1.4 Resumption of regorafenib dosing

When regorafenib is administered, if you develop diarrhea, fatigue, loss of appetite, nausea, vomiting, and other adverse events judged by your doctor as Regorafenib (excluding asymptomatic test values) that cannot deny the causal relationship with Regorafenib, "Table 6.3.1.4 Dose Adjustment for Other Adverse Events ", the investigational physician judges and adjusts the dose.

| NCI CTCAE Grade | Possibility to continue | Dose adjustment | | | |
|-----------------|-------------------------------|------------------|--|--|--|
| | administration | | | | |
| Grade 2 | Continue administration | No change | | | |
| Grade 3 | Weigh out until recovering to | Reduce one level | | | |
| | Grade 2 or lower | | | | |
| Grade 4 | Discontinue administration | — | | | |

Table 6.3.1.4 Dose Adjustment for Other Adverse Events

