| relationship | | at the discretion of the | the last dose. | |
| | | attending physician | | |
| | 3 or severe | Toxicity is returned to | Terminate nivolumab when the subject | |
| | | below grade 1 | does not recover from toxicity within 12 | |
| | | | weeks of the last dose, or when | |
| | | | corticosteroids cannot be decreased to | |
| | | | <10 mg/day of prednisolone within 12 | |
| | | | weeks. | |
| | 4 | Nivolumab termination | Nivolumab termination | |

Note: In the event that severe or \geq grade 3 side effects recur or when life-threatening toxicity develops, administration of the investigational drug will be terminated.

a. In patients with liver metastasis and HCC, any treatment for grade 2 AST and/or and ALT elevation will be resumed, and nivolumab treatment will be terminated when AST and/or ALT levels continue to be 50% higher than at baseline for \geq 1 week.

b. If the subject recovers from symptoms within 1 h of dose suspension, the dose will be resumed at an infusion rate of 50% of the initial rate (e.g., 50 mL/h from 100 mL/h). If the subject does not recover from symptoms within 1 h of dose suspension, the dose will be withdrawn until the symptoms recover and pretreatment will be administered at the time of the next dose. Refer to 6.3.2.1 for details.

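### Minor wording error in Table 5: read literally, the first grade 3 regorafenib hold ends when one of AST and ALT has recovered, even if the other is still above 5 times the upper limit of normal

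*Combined protocol and SAP*

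**What the plan says.** Table 5 in Section 6.3.1.3 adjusts regorafenib for raised AST, ALT or total bilirubin when a causal link cannot be ruled out.

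- **Entry to grade 3.** Bilirubin above 3 and up to 10 x ULN, or the enzyme condition: "If AST or ALT exceeds 5 times the normal value upper limit and is 20 times or less". Either enzyme is enough.
- **First grade 3 event.** Regorafenib is withheld until bilirubin is below 1.5 x ULN "and AST or ALT is recovered to less than 3 times normal value upper limit or below registered Grade". The restart wording is garbled, but appears to mean the same dose or one level lower. Weekly AST, ALT and bilirubin are recommended for at least 4 weeks.
- **Second grade 3 event, or any grade 4 event.** Regorafenib is discontinued.
- **Grade 2.** Dosing continues, and weekly monitoring runs for at least 4 weeks, until bilirubin is below 1.5 x ULN and "AST or ALT is less than 3 times upper limit of normal value or recovered to Grade before administration". The same 'or' appears here, but it governs only how long monitoring lasts.

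**The concern.** In the entry cell 'or' is correct, because one high enzyme should stop the drug. The same conjunction in the release cell reverses the protection: one low enzyme can end the hold. A patient could then go back on regorafenib with the other enzyme anywhere from 3 to 20 x ULN, and so possibly still at grade 3.

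What is at stake is patient safety in a dosing rule. Section 2.6.2 lists one acute liver failure among 17 deaths for which an association with regorafenib could not be denied, against a background of about 4,000 safety reports. That shows why liver rules matter for this drug. It is not a rate, and it says nothing about restarts with one enzyme still high.

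The wording also blurs the next line of the table. Discontinuing at the second grade 3 event requires a clear end to the first. A hold that ends while ALT is still at grade 3 does not provide one.

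**Working it through.** The plan gives no figure to reproduce, so this is a check of logic.

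**Conditions, from Table 5**

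- Entry (enzymes): AST > 5 x ULN OR ALT > 5 x ULN, up to 20 x.
- Release as printed: bilirubin < 1.5 x ULN AND (AST recovered OR ALT recovered).
- Release as very probably meant: bilirubin < 1.5 x ULN AND AST recovered AND ALT recovered.
- Recovered: < 3 x ULN, or below the grade at registration.

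**Illustrative values**, with bilirubin at 1.0 x ULN and both enzymes normal at registration:

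| AST (x ULN) | ALT (x ULN) | Entry condition still met? | Release as printed | Release if both must recover |
|---|---|---|---|---|
| 2.5 | 12 | yes | restart allowed | hold |
| 12 | 2.5 | yes | restart allowed | hold |
| 2.5 | 4 | no (grade 2) | restart allowed | hold |
| 2.5 | 2.5 | no | restart allowed | restart allowed |
| 4 | 4 | no (grade 2) | hold | hold |
| 12 | 12 | yes | hold | hold |

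The two readings differ exactly when one enzyme has recovered and the other has not. In the first two rows the printed release condition and the entry condition of the same table row are true together.

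**An extreme case.** Suppose bilirubin stays normal, AST never rises and ALT reaches 8 x ULN. AST is already below 3 x ULN on the day the hold begins, so the printed release condition is met at once and the hold has no length.

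**Does other text supply the missing requirement?**

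- The introduction to Section 6.3.1.3 recommends weekly liver tests until results return to normal or to the enrollment grade. This sets test frequency, not a restart criterion.
- Section 6.2.1, criterion 3, ends treatment for treatment-related grade 4 non-haematological toxicity. It does not reach an enzyme between 5 and 20 x ULN.
- Section 6.3.1.4 covers "other adverse events judged by your doctor as Regorafenib (excluding asymptomatic test values) that cannot deny the causal relationship with Regorafenib", so it leaves out an enzyme rise without symptoms.
- Table 6 in Section 6.3.2 governs nivolumab.

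None of these requires both enzymes to recover before regorafenib restarts.

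**The case against.** The strongest reply is that the literal reading defeats itself. A hold that can be over at the moment it starts makes no sense, and a patient with ALT at 12 x ULN still belongs in the row that requires withdrawal. The natural reading is that whichever enzyme triggered the hold must come down. The English shows translation faults elsewhere in the dosing section, so one conjunction is weak evidence of the rule that sites follow. This stands as to intent. A reader might infer that the plan deliberately allows restart with one enzyme high, and the documents do not support that.

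The safeguards are also real:

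- The opening of Section 6 makes its rules conditional: "If the safety of the subject is not at risk, treatment and changes to treatment will be carried out in accordance with the content" of that chapter.
- Section 6.2.1, criterion 11, lets the attending physician end treatment. Nothing in Table 5 compels a restart.
- When nivolumab is a cause, Table 6 ends nivolumab at grade 3 to 4 enzymes, with an exception in footnote a for liver metastasis and hepatocellular carcinoma. Section 6.1 then leaves "continuing the treatment protocol with either nivolumab or regorafenib monotherapy upon deliberation with the trial coordinating committee".
- Section 6.3.2.1 provides steroids for grade 3 to 4 liver impairment suspected to be related to nivolumab.

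These narrow the exposed group mainly to toxicity attributed to regorafenib. They do not correct the release cell.

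A reader might also infer a second gap in the registered-grade alternative. Enrollment allows "≤ 250 U/L in patients with liver metastasis". On an assumed ULN of 30 to 45 U/L that is 250/45 = 5.6 to 250/30 = 8.3 x ULN, already grade 3, so a return to grade 3 would say little about recovery. But the cell says below the registered grade. For a patient registered at grade 3, that means grade 2 or lower, at most 5 x ULN. The gap appears only if the text is relaxed to at or below. The grade 2 cell does speak of recovery to the pre-treatment grade, so there is some ambiguity, but no demonstrated error.

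Nor do the documents support capping each enzyme at its registration value. For that patient the cap would be looser than the printed limit (up to 8.3 x rather than 5 x). It would also be stricter than footnote a, under which "nivolumab treatment will be terminated when AST and/or ALT levels continue to be 50% higher than at baseline" for at least a week: 1.5 x 250 = 375 U/L from a baseline of 250.

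**Conclusion.** The release condition is wrong as written, and the point is minor. It is almost certainly a drafting or translation slip, in the only rule for restarting regorafenib after grade 3 liver enzymes. Harm would require a patient whose AST and ALT diverge, with bilirubin below 1.5 x ULN, and a clinician who applies the cell literally. The documents give no data on how often that would happen, so no frequency is claimed.

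A reader might infer that the trial's results are at risk. They are little or not affected. Section 6.1.3 in general counts non-haematological toxicity of grade 3 or more as a DLT, subject to its listed exceptions, so the first event is largely captured whatever the restart rule says. The efficacy analyses do not use this rule.

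The conclusion rests on the printed text and on reading the garbled restart instruction as the same dose or one level lower. It does not depend on an assumed ULN.

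**What to change.** In the grade 3 release cell of Table 5, require that *both AST and ALT are recovered*, keeping the bilirubin limit, the 3 x ULN limit and the registered-grade alternative as printed. Make the same change in the grade 2 cell, where it affects monitoring only.

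No tests are added: Table 8.1 already lists AST, ALT and total bilirubin together, and Table 8.2 schedules biochemistry at screening and at the treatment visits. Sites that already read the rule as intended will see no change. At any site reading it literally, some holds would last longer, which is the purpose.

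Section 13.4.4 provides a memorandum or Q&A to reduce differences in interpretation, so the clarification could go out that way first. The table text can then be corrected at the next protocol revision, with the site and IRB approvals that Sections 13.4.4 and 13.4.5 require.

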6.3.1.4 Resumption of regorafenib dosing

When regorafenib is administered, if you develop diarrhea, fatigue, loss of appetite, nausea, vomiting, and other adverse events judged by your doctor as Regorafenib (excluding asymptomatic test values) that cannot deny the causal relationship with Regorafenib, "Table 6.3.1.4 Dose Adjustment for Other Adverse Events ", the investigational physician judges and adjusts the dose.

| NCI CTCAE Grade | Possibility to continue | Dose adjustment | | | |
|-----------------|-------------------------------|------------------|--|--|--|
| | administration | | | | |
| Grade 2 | Continue administration | No change | | | |
| Grade 3 | Weigh out until recovering to | Reduce one level | | | |
| | Grade 2 or lower | | | | |
| Grade 4 | Discontinue administration | — | | | |

Table 6.3.1.4 Dose Adjustment for Other Adverse Events

6.3.2 Criteria for changing the nivolumab dosage

Adverse events (irrespective of severity) associated with nivolumab exposure might be of immunological etiology. Such adverse events can occur immediately following the commencement of treatment with the investigational drug or several months after completion of treatment. For toxicities and severe or life-threatening adverse events with a causal relationship with nivolumab, the withdrawal and termination of nivolumab will be carried out in accordance with Table 6.3.2. For the guidelines regarding supportive therapy, including the use of corticosteroids, refer to section 6.3.2.1, and the investigator brochure (appendix 3 Management Algorithms).

In accordance with the instructions given in this section, administration is withdrawn and administration resumed. Subjects whose resumption of Nivolumab and Regorafenib need to be delayed for more than 28 days from the scheduled start date will cease protocol treatment. However, administration of Regorafenib was discontinued, but when Nivolumab resumption is possible according to 6.3.2, protocol treatment can be restarted with Nivolumab alone.

| Toxicity | Grade | Timing of | treatment | Instance | requiring | nivolumab |
|------------------|------------|----------------|-----------|--------------------------------------|-------------------|---------------|
| | requiring | resumption | after | termination | | |
| | withdrawal | withdrawal | | | | |
| Diarrhea/colitis | 2–3 | Toxicity is re | turned to | Terminate nivolumab when the subject | | n the subject |
| | | below grade | 1 | does not reco | over from toxic | ity within 12 |
| | | | | weeks of the | e last dose, or v | vhen |
| | | | | corticostero | ids cannot be d | ecreased to |
| | | | | below 10 mg | g/day of predni | solone |

Table 6: Criteria for nivolumab withdrawal and termination

| | | | within 12 weeks. |
|-------------------|----------------|-------------------------------------|--|
| | 4 | Nivolumab termination | Nivolumab termination |
| Elevated AST, | 2 | Toxicity is returned to | Terminate nivolumab when the subject |
| ALT, and/or | | below grade 1 | does not recover from toxicity within 12 |
| bilirubin | | | weeks of the last dose. |
| | 3-4 | Nivolumab termination | Nivolumab termination. |
| | | (see exceptions below) ^a | |
| Type I diabetes | T1DM | When clinically and | Terminate nivolumab when the subject |
| (T1DM: when | or 3–4 | metabolically stable | is not clinically and metabolically stable |
| newly | | | within 12 weeks of the last dose. |
| developed) or | | | |
| hyperglycemia | | | |
| Hypophystitis | 2–4 | Toxicity is returned to | Terminate nivolumab when the subject |
| | | below grade 1. | does not recover from toxicity within 12 |
| | | When endocrine | weeks of the last dose, or when |
| | | hormone replacement | corticosteroids cannot be decreased to |
| | | therapy has been | below 10 mg/day of prednisolone |
| | | initiated. | within 12 weeks. |
| Hyperthyroidism | 3 | Toxicity is returned to | Terminate nivolumab when the subject |
| | | below grade 1 | does not recover from toxicity within 12 |
| | | | weeks of the last dose, or when |
| | | | corticosteroids cannot be decreased to |
| | | | <10 mg/day of prednisolone within 12 |
| | | | weeks. |
| | 4 | Nivolumab termination | Nivolumab termination |
| Hypothyroidism | Not | When thyroid hormone | |
| | stipulated | replacement therapy | |
| | | has been initiated | |
| Infusion reaction | 2 ^b | Toxicity is returned to | Terminate nivolumab when toxicity |
| | | below grade 1 | develops despite appropriate |
| | | | pretreatment. |
| | 3-4 | Nivolumab termination | Nivolumab termination |
| Pneumonitis | 2 | Toxicity is returned to | Terminate nivolumab when the subject |
| | | below grade 1 | does not recover from toxicity within 12 |
| | | | weeks of the last dose, or when |

| | | | corticosteroids cannot be decreased to | |
|-------------------|-------------------------------------|--------------------------|---|--|
| | | | <10 mg/day of prednisolone within 12 | |
| | | | weeks. | |
| | 3-4 | Nivolumab termination | Nivolumab termination | |
| Renal | 2 | Toxicity is returned to | Terminate nivolumab when the subject | |
| impairment or | | below grade 1 | does not recover from toxicity within 12 | |
| nephritis | | | weeks of the last dose, or when | |
| | | | corticosteroids cannot be decreased to | |
| | | | <10 mg/day of prednisolone within 12 | |
| | | | weeks. | |
| | 3-4 | Nivolumab termination | Nivolumab termination | |
| All other | Intolerance | The decision to | Terminate nivolumab when the toxicity | |
| toxicities with a | or persistent withdraw and resume g | | persists after drug withdrawal and is not | |
| causal | 2 | nivolumab can be made | returned <grade 1="" 12="" from<="" td="" weeks="" within=""></grade> | |
| relationship | | at the discretion of the | the last dose. | |
| | | attending physician | | |
| | 3 or severe | Toxicity is returned to | Terminate nivolumab when the subject | |
| | | below grade 1 | does not recover from toxicity within 12 | |
| | | | weeks of the last dose, or when | |
| | | | corticosteroids cannot be decreased to | |
| | | | <10 mg/day of prednisolone within 12 | |
| | | | weeks. | |
| | 4 | Nivolumab termination | Nivolumab termination | |

Note: In the event that severe or \geq grade 3 side effects recur or when life-threatening toxicity develops, administration of the investigational drug will be terminated.

a. In patients with liver metastasis and HCC, any treatment for grade 2 AST and/or and ALT elevation will be resumed, and nivolumab treatment will be terminated when AST and/or ALT levels continue to be 50% higher than at baseline for \geq 1 week.

b. If the subject recovers from symptoms within 1 h of dose suspension, the dose will be resumed at an infusion rate of 50% of the initial rate (e.g., 50 mL/h from 100 mL/h). If the subject does not recover from symptoms within 1 h of dose suspension, the dose will be withdrawn until the symptoms recover and pretreatment will be administered at the time of the next dose. Refer to 6.3.2.1 for details.

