4 INCLUSION AND EXCLUSION CRITERIA

4.1 Inclusion criteria

- 1. Patients who provided written informed consent to be subjects in this trial
- 2. Patients at least 20 years of age on the day of providing consent
- Dose-escalation cohort: Patients with histologically or cytologically confirmed advanced or metastatic solid tumors.

Expansion cohort: Patients with histologically or cytologically confirmed advanced or metastatic solid tumors (gastric, colorectal, or hepatocellular cancer).

- 4. Patients with an Eastern Cooperative Oncology Group (ECOG) performance status (PS) of 0 or 1
- 5. Patients capable of taking oral medication
- 6. Patients with evaluable or measurable lesions as per RECIST version 1.1
- Patients with adequate organ function at the time of enrollment as defined below: [Acceptable 7 days examination before the same day of the registration date]
 - Neutrophil count $\geq 1500/\text{mm}^3$
 - Platelet count $\geq 10.0 \times 10^4$ /mm³ (transfusion >2 weeks before testing permitted)

• aspartate transaminase (AST), alanine transaminase (ALT) $\leq 100 \text{ U/L2.5-times}$ the upper limit of normal (200U/L I patients with hepatocellular cancer ,or $\leq 250 \text{U/L}$ in patients with liver metastasis)

- Total bilirubin ≤ 1.5 -mg/dL
- Creatinine ≤ 1.5 -times the upper limit of normal
- Urinary protein: It satisfies one of the following (if any of the inspection criteria are satisfied, other examination may not be carried out)
 - (i) urinary protein (test paper method) is 2+ or less
 - (ii) UPC (Urine Protein Creatinine) ratio <3.5
 - (iii) 24-hour urine protein was measured, urinary protein $\leq 3500 \text{ mg}$
 - PT-INR: $\leq 1.5 \ (\leq 3.0 \text{ in case of anticoagulant administration})$
 - * It is Child A in the case of Expansion cohort's hepatocellular carcinoma
- 8. For women who are likely to become pregnant (including those without menstruation due to medical reasons such as chemical menopause) Note 1, we agreed to double contraceptive Note 2 for at least 5 months after the final administration of the investigational product from consent acquisition patient. Also, patients who agreed not to breast feeding for at least 5 months after the final investigational drug administration after acquiring consent.

For men, patients agreeing to double contraceptive for at least 7 months after the final investigational drug administration from the time of starting investigational drug administration.

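### Footnote a of Table 6 is attached to the grade 3-4 liver-enzyme row but describes grade 2, and its 50%/1-week nivolumab stopping clause has no stated scope

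*Combined protocol and SAP*

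**What the plan says.** Table 6 (Section 6.3.2) has two rows for elevated AST, ALT and/or bilirubin.

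- **Grade 2.** Withhold nivolumab until the toxicity is back below grade 1. Terminate if the subject "does not recover from toxicity within 12" weeks of the last dose. This row carries no footnote marker.
- **Grade 3-4.** Terminate nivolumab, with the remark "see exceptions below" and marker a.

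Footnote a is the text that marker leads to. It opens "In patients with liver metastasis and HCC, any treatment for grade 2 AST and/or and ALT elevation will be resumed", and continues that "nivolumab treatment will be terminated when AST and/or ALT levels continue to be 50% higher than at baseline for" 1 week or more. It does not mention grade 3 or 4, and it does not refer to the 12-week limit.

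The text above the table sets a further limit: subjects whose resumption of nivolumab and regorafenib would "need to be delayed for more than 28 days from the scheduled start date will cease protocol treatment". Section 6.2.1 also lists a 28-day limit.

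**The concern.** An exception should say what it is an exception to. This one hangs on the row for immediate termination at grade 3-4, but its wording deals with grade 2, which has its own row and a different rule. An investigator treating a patient with liver metastasis or HCC cannot tell from the text whether nivolumab is withheld, resumed or ended.

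Such patients are to be expected. The expansion cohort is gastric, colorectal and hepatocellular cancer, dose escalation takes any solid tumor, and the entry limits for liver enzymes are raised for liver metastasis (and, in Section 4.1, for HCC). Sites that resolve the conflict differently would give different nivolumab exposure to similar patients. In cycle 1 of dose escalation the difference can reach the primary endpoint, because Section 6.1.3 counts a nivolumab dose that cannot be given because of toxicity as a DLT.

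**Working it through.** The plan gives no figure to reproduce. The check compares the rules and then locates the 50% trigger on the protocol's own grade scale.

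**1. The rules side by side, for a patient with liver metastasis or HCC**

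| Situation | Table row | Footnote a |
|---|---|---|
| Grade 2, next dose due | Withhold until below grade 1 | Treatment is resumed; no recovery condition |
| Grade 2, persisting | Terminate after 12 weeks (12 × 7 = 84 days) from last dose | Terminate after 1 week (7 days) at 50% above baseline |
| Grade 3-4 | Terminate, subject to the exception | Grade not mentioned |

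The 28-day limit runs on another clock. If the scheduled date is the next two-weekly dose, it is reached 14 + 28 = 42 days after the last dose, half of the 84 days in the grade 2 row. It can also be read as applying only when both drugs are delayed.

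**2. Inputs for the trigger**

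- Grade 2 band, from Table 5 in Section 6.3.1.3: "If AST or ALT exceeds 3 times the normal value upper limit and is 5 times or less".
- Grade 3 band, same table: "If AST or ALT exceeds 5 times the normal value upper limit and is 20 times or less".
- ULN: not stated. Section 4.1 runs a limit of 100 U/L together with 2.5 times ULN, which implies 100 / 2.5 = 40 U/L. This is an assumption; 30 to 50 U/L is shown as a range.
- Trigger value: 1.5 × baseline B.

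**3. Where the trigger falls if the clause is read with no grade limit**

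- Not above the lower limit of grade 2: 1.5B ≤ 3 × ULN, so B ≤ 2 × ULN = 80 U/L (60 at ULN 30; 100 at ULN 50).
- Above the grade 2 band: 1.5B > 5 × ULN, so B > 3.33 × ULN = 133 U/L (100; 167).

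| Baseline (U/L) | 1.5 × baseline (U/L) | Multiple of ULN 40 | Grade |
|---|---|---|---|
| 40 | 60 | 1.5 | 1 |
| 80 | 120 | 3.0 | 1 |
| 100 | 150 | 3.75 | 2 |
| 160 | 240 | 6.0 | 3 |
| 200 | 300 | 7.5 | 3 |
| 250 | 375 | 9.4 | 3 |

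On this reading the clause is stricter than the grade 2 row at low baselines and looser than the grade 3-4 row at high ones.

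**4. Where it falls if the clause is limited to grade 2**

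- *Grade 2 reached on treatment.* For B ≤ 80 U/L, every grade 2 value (above 120 U/L) is already more than 50% above baseline, since 1.5 × 80 = 120. Any grade 2 elevation lasting a week then ends nivolumab, against 84 days in the row. For B > 133 U/L the trigger exceeds 200 U/L (5 × 40), so it can never be met within grade 2.
- *Grade 2 already at baseline.* B > 3 × ULN gives a trigger above 4.5 × ULN, or 180 U/L.

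Neither narrower reading removes the conflict in step 1.

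**5. Entry limits**

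Section 4.1 admits 200 U/L in HCC (the Section 1 summary says 100) and 250 U/L with liver metastasis. At ULN 40 these are 200 / 40 = 5 and 250 / 40 = 6.25 times ULN, the top of grade 2 and inside grade 3. Neither row of Table 6 refers to baseline, whereas Table 5 for regorafenib does.

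**6. Reach into the DLT assessment**

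Table 8.2 schedules blood tests on days 8 and 15 of cycle 1 and nivolumab on day 15. For an affected patient at grade 2 on day 15, the row withholds the dose, which may count as a DLT under Section 6.1.3; the footnote's first clause gives it. If the enzymes were 50% above baseline on both days (15 − 8 = 7 days), the footnote's second clause ends nivolumab.

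**The case against.** A rule for a named subgroup may properly differ from the general row, so difference alone is not contradiction. That stands. The defect is unstated scope, not the existence of a subgroup rule.

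Three stronger readings are tempting, and the documents do not support them.

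- *That the footnote was meant to relax the 12-week rule and tightens it instead.* The marker is on the grade 3-4 row; the row with the 12-week rule has none. Nor is the footnote always the stricter rule: above a baseline of 133 U/L (ULN 40), a 50% rise is already grade 3, where the marked row would terminate at once.
- *That the clause has no grade floor, so that a rise from 30 to 45 U/L for a week ends nivolumab.* This is one literal reading. The sentence opens with grade 2, the table's liver-enzyme entry starts at grade 2, and 45 U/L is only 45 / 40 = 1.1 times the assumed ULN.
- *That half or more of the roughly 30 expansion patients would be affected.* The documents give no share with HCC or liver metastasis, and having the diagnosis is not the same as stopping nivolumab.

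There are also softening provisions. Regorafenib alone may continue after deliberation (Section 6.1), the coordinating committee can reconsider protocol-treatment termination case by case (Section 6.2.1), and DLTs are finally settled by deliberation (Section 6.1.3). Section 6.3.2 also points to management algorithms in the investigator brochure, which are not available here, but cites them for supportive therapy. None of these says which row governs.

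**Conclusion.** The point holds as a conflict of scope within a treatment-stopping rule. For patients with liver metastasis or HCC at grade 2, the row and the footnote give incompatible instructions: withhold against resume, and 84 days against 7. At grade 3-4 the marked exception says nothing usable. These findings come from the text alone.

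The baseline thresholds (80 and 133 U/L, ranging over 60 to 100 and 100 to 167) rest on an assumed ULN of 40 U/L (30 to 50) and on the literal reading of the 50% clause. They show how far the meaning shifts with interpretation; they do not predict how many patients would stop treatment.

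No sample size, power, alpha or planned analysis depends on the clause. The consequences are inconsistent nivolumab exposure in an expected patient group and possible inconsistency in cycle 1 DLT calls. That is enough to justify correction.

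**What to change.** Reconcile footnote a, the grade 2 row, the grade 3-4 row and the 28-day delay limit in Section 6.3.2, so that one rule governs each grade and baseline level in patients with liver metastasis or HCC. The revised text should state:

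- which on-treatment grade, and which baseline grade, the 50%/1-week clause covers;
- whether it replaces or adds to the 12-week rule and the grade 3-4 termination rule;
- how the 28-day limit relates to both.

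Place the marker on the row or rows that the footnote modifies. The HCC entry limit (Section 1 against Section 4.1) should be aligned at the same time, since it determines which baselines occur. The clinical team decides the content of the rule.

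The cost is a rewritten footnote with matching edits to two table rows and one sentence. No analysis changes.
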